
## **Randomization**

[name] or [name] will oversee the randomization to either CE+ISR or CE+PBO conditions. Both participants and study personnel will be blind to study condition, and study medication will be labeled by either "A" or "B" by the pharmacy in order to blind the medication administration. A random number generator will be used to assign individuals to either condition. Only [name] or [name] will have the information necessary to break the blind. Prior to data analyses, [name] will check the balance of randomization and control for any factors that are imbalanced.

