## **Intervention Modules**

***Abstinence Challenge.*** Eligible participants will be required to abstain from smoking beginning 24 hours prior to the physical exam that occurs on the day of the first CE session and up until the time of the second session. Abstinence status will be verified by a Vitalograph Breathco Carbon Monoxide monitor ( $\leq 4$  ppm). If a participant is not abstinent at the time of the physical exam and CE session 1, the participant will be asked to re-schedule within 1 week. In order to ensure compliance with alcohol abstinence 24 hours prior to CE session 1 and 24 hours after CE session 1, abstinence status will be verified by an AlcoBreath measurement at the beginning of CE session 1 and the beginning of CE session 2. If a participant is not abstinent at the time of CE session 1, the participant will be asked to re-schedule within 1 week.

***Ecological Momentary Assessment (EMA).*** Eligible participants will be asked to respond to surveys delivered via text message or email up to 15 times per day 24-hours prior to the physical exam and up until the time of Cue Exposure Session 2 (48 hours total). Participants will be asked various questions related to smoking craving, behavior, and cues (see attached Short Smoking Log).

***Cue Exposure (CE).*** The two 60-minute CE sessions will be conducted to expose participants to interoceptive and situational cues for tobacco use and craving (see Cue Exposure Therapy Protocol attachment). In the first session, participants will receive a dose of ISR or PBO and begin the CE session after waiting 75 minutes. The overarching goal of CE is to expose participants to triggers that will produce high cravings, and to repeat exposure to those triggers in a controlled setting in order to allow the craving to come down on its own. Because not all smokers respond equally to the same triggers, clinicians are trained to apply a variety of approaches. These can include exposure to slides, videos (on a traditional flat screen as well as in 360 video headsets) depicting smoking cues (visual exposure), exposure to emotions and imagined situations that most reliably triggered an urge to smoke (emotional/imaginal), and exposure to a participant's own cigarettes (in vivo). The second session will be conducted 24 h after the first in a medication-free state. Clinicians will record craving throughout the CE sessions (see Reported Craving During CE attachment).

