***Isradipine or Placebo.*** All capsules will be identical in appearance to maintain the blind design of the study. Study capsules will be prepared containing: (a) 15 mg immediate release isradipine or (b) pill placebo. Individual doses of study medications, prescribed by [name], will be dispensed to patients by study personnel 75 minutes prior to CE 1 and patients will be asked to remain in the clinic until session time. Because all pill taking is observed, no pill counts are necessary to help ensure adherence to the randomized drug condition. The drug will be prepared at Abrams Royal ([name]). All medications will be stored in a locked refrigerator. Upon completion of recruitment, unused medication will be returned to the pharmacy for proper disposal.

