***Measures of research integrity, safety, and acceptance***

**Vital Signs.** Participants' blood pressure and heart rate will be assessed. This will be collected during the screening visit, CET visit 1 and 2.

**Patient Adherence.** Patient adherence will be assessed by taking attendance at each session.

**Researcher Adherence.** Each session (for those participants who give consent to be videotaped) will be videotaped and 10% will be rated shortly thereafter by independent raters to assess therapist adherence to, and competence with, the experimental protocol. Participants are not required to be videotaped and will indicate on their ICD whether or not they are willing to participate in the recording of sessions. Sessions from CE visit 1 and 2 will be reviewed.

**Concurrent Treatment.** Use of medications other than nicotine patch or other aids to smoking cessation and participation in any concurrent psychotherapeutic treatment will be assessed. This will be collected during the screening visit, CE visit 1 and 2.

**Safety Monitoring and Concerns.** At each visit, participants will be asked about side effects of the study medication and procedures. Adverse Events forms will be utilized to track any symptoms expressed during study visits. Forms will be reviewed each visit by the study PI, and participants who report significant symptoms or adverse reactions will be interviewed separately. This will be collected during the screening visit, CE visit 1 and 2.

**AlcoBreath Screening.** Participants will be asked to breathe into an AlcoBreath tube in order to assess for the presence of alcohol. Although there are no absolute contraindications to co-administration of isradipine with alcohol, both substances are metabolized through the liver. Participants are advised to refrain from alcohol for at least 24 hours prior to administration of isradipine and 24 hours after administration of isradipine. This will be collected during the screening visit, CE visit 1 and 2.

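### The clinicians who deliver cue exposure also record the Aim 1 craving ratings, and the visible text does not separate them from vital signs and side-effect reports gathered at the dosing visit

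*Combined protocol and SAP*

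**What the plan says.** **Who delivers and who records.** The Cue Exposure paragraph of Intervention Modules gives clinicians discretion over delivery: "Because not all smokers respond equally to the same triggers, clinicians are trained to apply a variety of approaches". The same paragraph assigns the outcome record to them: "Clinicians will record craving throughout the CE sessions (see Reported Craving During CE attachment".

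**What the ratings decide.** Under Data Analyses, Specific Aim 1, the test is the Group by Trial interaction on craving, using the first and last trials of CE session 2. Two recorded numbers per participant enter that test.

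**What else is collected around dosing.** Under the measures of research integrity, safety and acceptance, the Vital Signs entry reads "Participants' blood pressure and heart rate will be assessed. This will be collected during the screening visit, CET visit 1 and 2", and the Safety Monitoring entry reads "At each visit, participants will be asked about side effects of the study medication and procedures". On adverse event forms it says "Forms will be reviewed each visit by the study PI". Neither entry names the person who measures or asks, and neither limits who else sees the results.

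**What protects the blind.** Randomization states: "Both participants and study personnel will be blind to study condition, and study medication will be labeled by either 'A' or 'B' by the pharmacy". It adds that only two designated people "will have the information necessary to break the blind". The Isradipine or Placebo paragraph adds: "All capsules will be identical in appearance to maintain the blind design of the study".

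**How the blind is checked.** One perceived-treatment item is put to participants, at CE visit 2 in the Assessment Schedule. There is no matching item for clinicians.

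**The concern.** The stated protections conceal the allocation code and the identity of the capsule. They do not address functional unblinding, in which someone works out the arm from what the drug does. The comparator is a pill placebo, and the plan has staff discuss possible isradipine side effects with participants before dosing. If the active drug changes blood pressure or pulse, or causes side effects a participant notices, information collected at or after dosing points towards the arm.

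A clinician who comes to suspect the arm can influence CE 2 in three ways: the cues chosen, the prompting during exposure, and the number written down. If any of these differs by arm, the Group by Trial contrast is biased, in either direction. It could create an apparent benefit or mask a real one. Such bias cannot be removed at analysis, and without a clinician treatment guess it would not be detected.

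**Working it through.** **Step 1: the plan's own figure.** Inputs from Sample size and power considerations: f = 0.1, alpha 0.05, power 80%, correlation 0.75, total N = 102 (51 per group), two trials (m = 2). For the within-between interaction:

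- Noncentrality λ = f² × N × m / (1 − ρ) = 0.01 × 102 × 2 / 0.25 = 8.16, with 1 and 100 degrees of freedom.
- Power at N = 102 is 0.808; at N = 100 it is 0.7997. So 102 is the smallest even total that reaches 80%, and the stated figure reproduces.

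**Step 2: the same effect as a difference in change.** With two groups and two trials, f = 0.1 corresponds to a between-arm difference in first-to-last change of 4 × 0.1 = 0.40 SD of a single rating.

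- SD of change = √(2 × (1 − 0.75)) = 0.707.
- Standard error of the between-arm difference = 0.707 × √(2/51) = 0.140.
- (0.40 / 0.140)² = 8.16, which agrees with step 1.

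**Step 3: an assumed bias with no drug effect.** Let b be the average between-arm shift in first-to-last change caused by delivery or recording. The test then has noncentrality 8.16 × (b/0.40)². The documents give no value for b, so these are assumed:

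| b (SD of one rating) | Noncentrality | False-positive rate at nominal 5% |
|---|---|---|
| 0 | 0 | 5.0% |
| 0.05 | 0.1275 | 6.4% |
| 0.10 | 0.51 | 10.9% |
| 0.20 | 2.04 | 29.3% |

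A bias one quarter of the design effect (0.10/0.40) more than doubles the error rate, because the trial is sized for a small effect.

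**Step 4: what kind of bias counts.** If a clinician's expectation adds the same amount c to both ratings, the change is (last + c) − (first + c) = last − first, and nothing reaches the primary contrast. Only an influence that differs between the first and last CE 2 trials matters.

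**Step 5: how large b must be per participant.** b is an arm-wide average. If, say, one third of active-arm participants showed a recognisable sign, b = 0.20 would need 0.20 × 3 = 0.60 SD in each of them, more than the 0.40 SD design effect; b = 0.10 would need 0.30 SD. The top row of the range therefore requires a strong influence.

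**Step 6: safeguards set against the route of concern.**

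| Safeguard | What it covers | Prevents or detects a clinician inferring the arm from drug effects? |
|---|---|---|
| Identical capsules | Appearance | No |
| A/B labels, restricted code | Allocation code | No |
| Stated blind of participants and personnel | Intention | States the aim; no procedure for drug effects |
| Independent raters, 10% of videotaped sessions | Adherence and competence at CE 1 and CE 2 | May show drift in delivery; craving is not re-rated |
| Perceived-treatment item | Participant's guess | Does not ask clinicians |

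**The case against.** The strongest reply is that the route to bias is pieced together from facts the documents do not state. Most of that stands.

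- **Timing.** Vital signs are listed for CE visit 1 without a time relative to dosing, and the Abstinence Challenge paragraph puts the physical exam on the same day. If the CE 1 readings precede the capsule, they say nothing about arm. The side-effect question is less exposed to this reply, because at CE 2 it necessarily follows dosing.
- **People.** No assessor is named for the CE 1 vital signs or side-effect questions, and adverse event forms go to the PI. Nothing says that CE clinicians collect these data, or that one clinician runs both sessions.
- **Unseen attachments.** The Cue Exposure Therapy Protocol and the craving form are cited but were not available, and either might settle staff roles and the rating procedure.
- **Nature of the outcome.** Craving is the participant's own report, and the text does not say how it is elicited. The clinician's influence is therefore indirect, and a bias that is equal at both trials cancels.

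A reader might infer that the blind rests on identical capsules alone, or that a clinician who saw a fall in blood pressure at CE 1 goes on to rate the same participant at CE 2. The documents do not support either reading. Randomization adds labelling, restricted code access and a stated blind of personnel, and the second scenario needs post-dose readings, clinician access to them and the same clinician on both days, none of which is stated.

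What the reply does not remove is that the text gives delivery and outcome recording to the same people and places no barrier between them and the safety data.

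**Conclusion.** The point holds as a risk of bias, not as demonstrated bias. Clinicians with discretion over exposure record the deciding ratings, the visible text does not separate them from drug-effect information, and the existing safeguards neither prevent nor would detect a clinician's inference of arm.

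The size is illustrative: about 6%, 11% or 29% false positives for assumed shifts of 0.05, 0.10 or 0.20 SD, given N = 102, correlation 0.75 and no true effect. This rests on three assumptions: isradipine produces signs that can be recognised, the information reaches the CE clinician, and the resulting influence differs between the first and last CE 2 trials. The sample size is unaffected. The change is a cheap improvement and has to be made prospectively.

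**What to change.** - **Intervention Modules, Cue Exposure.** Have the participant enter the craving ratings directly, on a tablet or paper, at least for the first and last trials of CE 2. When a headset is in use, take the rating between exposures. The clinician may see the ratings in order to run the session.
- **Vital Signs and Safety Monitoring.** State who collects these data and when. Have any vital signs taken after dosing at CE 1, and the CE 1 and CE 2 side-effect questions, handled by existing staff not running that participant's exposure. Keep those forms from the CE clinician until the last CE 2 rating is entered, except where participant safety requires otherwise.
- **Optional check.** Ask the CE clinician for a treatment guess before and after CE 2.

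The documents already mention a study nurse, research assistants and an iPad, although the iPad is mentioned only for consent. If the unseen attachments already provide this separation, a cross-reference is enough.

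The cost is minor scheduling and a brief pause for self-entry. Self-entry addresses recording but not cue choice or prompting, so both main changes are needed. Neither removes bias from the participant's own guess of treatment.

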## **SUMMARY OF VISITS**

	Physical Exam	Cue Exposure Day 1	Cue Exposure Day 2
Length:	30 minutes	2.5 hours	1 hour

Purpose:	
 
- Ecological Momentary Assessment 24-hours prior to Day 1 visit (text)
 
-Determine your eligibility by ensuring that it is safe for you to take isradipine.
 
- Receive \$10 cash payment.
 
	
 
-Take isradipine or placebo, wait 75 min, do 60 min of cue exposure.
 
- Receive \$30 for Day 1 and \$2 per EMA response (up to \$30), for a total of up to \$60 for Day 1.
 
	
 
- Ecological Momentary Assessment 24-hours prior to Day 2 visit (text)
 
- Do 60 min of cue exposure without taking isradipine or placebo (no medication).
 
- Receive \$50 for Day 2 and \$2 per EMA response (up to \$30), for a total of up to \$80 for Day 2.
 

-----------------	---	--	---

## Measures

### Assessment Instruments

#### **Screening Measures**

Initial Eligibility Screen. This questionnaire will assess some of the basic inclusion and exclusion criteria. This will be collected in the online prescreen.

Demographics. Participants will be asked to provide standard demographic information (i.e. age, gender, race/ethnicity, level of education, etc.) as well as history of medical problems. This will be collected in the online prescreen.

Suicide. The Columbia Suicide Severity Rating Scale (C-SSRS; Posner, Oquendo, Gould, et al. 2007) is a standardized measure of current and past self-injurious behavior, suicidal intent, and suicidal behaviors. The C-SSRS has demonstrated good reliability and validity (Hammond et al., 2006; Posner et al., 2007). The C-SSRS will be administered as part of the diagnostic interview in order to assess for a history of suicide attempts or current suicidal thoughts or plans. This will be collected during the screening visit. The IRB-approved standard operating procedures for individuals who pose a suicide risk will be followed (see attached Suicidality SOP).

Vital Signs. Temperature (Temp), pulse (P), respiratory rate (RR), and blood pressure (BP) will be obtained. This will be collected during the screening visit, CE visit 1 and 2.

Medical evaluation. A study advanced practice nurse will review the patient's medical history and conduct a complete physical examination if deemed necessary. This will be collected during the screening visit.

Overall Anxiety Scale (OAS/S): The OASIS is a 5 question self-report instrument that measures transdiagnostic anxiety symptoms (Norman et al., 2006).

#### **Measures of smoking behavior, nicotine dependence, withdrawal symptoms, and sleep measures**

Fagerström Test for Nicotine Dependence (FTND). The FTND is a 6-item scale designed to assess gradations in tobacco dependence (Heatherton et al., 1991). This measure will serve to quantify nicotine dependence, which will be used as a covariate in the primary analyses. This will be collected during the screening visit.

Minnesota Withdrawal Scale (MWS). Given its potential relation to outcome, we will monitor withdrawal severity using the Minnesota Withdrawal Scale, a reliable and sensitive 10-item scale (Hughes & Hatsukami, 1986). This will be collected at CE visit 1 and 2.

**Smoking Cue Appeal Survey (SCAS).** The Smoking Cue Appeal Survey (Murray, McHugh, Rowley, Sirota, & Otto, 2010) measures cue appeal to sensory smoking cues. An initial study demonstrated good psychometric properties associated with smoking status and craving (Murray et al., 2010). This will be collected during the screening visit, CE visit 1 and 2.

**Pittsburgh Sleep Quality Index (PSQI) and Sleep Diary.** The Pittsburgh Sleep Quality Index (Buysse, Reynolds, Monk, Berman, & Kupfer, 1989) is a self-reported questionnaire which assesses sleep quality and disturbances. The question items group into seven component scores: sleep quality, sleep latency, sleep duration, habitual sleep efficiency, sleep disturbances, use of sleep medication, and daytime dysfunction. In addition, a short self-report sleep diary will be administered in order to record the previous night's sleep. The sleep measures will be used to examine the impact of sleep on the efficacy of exposure therapy and may also be used as a covariate in primary analyses. The PSQI will be collected at CE visit 1 and the Sleep Diary will be collected at CE visits 1 and 2.

**Perceived Treatment.** A single self-reported item will be asked to examine whether the participant believes they received the active treatment study drug or a placebo.

***Measures of research integrity, safety, and acceptance***

**Vital Signs.** Participants' blood pressure and heart rate will be assessed. This will be collected during the screening visit, CET visit 1 and 2.

**Patient Adherence.** Patient adherence will be assessed by taking attendance at each session.

**Researcher Adherence.** Each session (for those participants who give consent to be videotaped) will be videotaped and 10% will be rated shortly thereafter by independent raters to assess therapist adherence to, and competence with, the experimental protocol. Participants are not required to be videotaped and will indicate on their ICD whether or not they are willing to participate in the recording of sessions. Sessions from CE visit 1 and 2 will be reviewed.

**Concurrent Treatment.** Use of medications other than nicotine patch or other aids to smoking cessation and participation in any concurrent psychotherapeutic treatment will be assessed. This will be collected during the screening visit, CE visit 1 and 2.

**Safety Monitoring and Concerns.** At each visit, participants will be asked about side effects of the study medication and procedures. Adverse Events forms will be utilized to track any symptoms expressed during study visits. Forms will be reviewed each visit by the study PI, and participants who report significant symptoms or adverse reactions will be interviewed separately. This will be collected during the screening visit, CE visit 1 and 2.

**AlcoBreath Screening.** Participants will be asked to breathe into an AlcoBreath tube in order to assess for the presence of alcohol. Although there are no absolute contraindications to co-administration of isradipine with alcohol, both substances are metabolized through the liver. Participants are advised to refrain from alcohol for at least 24 hours prior to administration of isradipine and 24 hours after administration of isradipine. This will be collected during the screening visit, CE visit 1 and 2.

***Assessment Schedule***

Participants will receive thorough assessments prior to and over the course of this study, summarized in the table below.

Measure (number of items)	Online/phone Screen	Daily monitoring until quit attempt	Physical Exam	CE visit 1	CE visit 2	
Initial eligibility screen	X					
Demographics	X					
Columbia Suicide Severity Rating Scale - CSSRS	X					
Overall Anxiety Scale OASIS (5)	X					
Fagerström Test for Nicotine Dependence - FTND (6)	X					
Medical history	X					
Carbon Monoxide (2)			X	X	X	
Minnesota Withdrawal Scale - MWS (15)				X	X	
Smoking Cue Appeal Survey -SCAS (8)	X			X	X	
Pittsburgh Sleep Quality Index - PSQI				X		
Sleep Diary				X	X	
Therapist Adherence				X	X	
Patient Adherence		X		X	X	
Adverse Events			X	X	X	
Vital Signs			X	X	X	
AlcoBreath			X	X	X	
Perceived Treatment					X	
Smoking log surveys		X				

## Data Analyses

### Specific Aim 1: Effect on Long Term Craving

To examine effects on the target of engagement, we will test the hypothesis that CE+ISR, compared to CE+PBO, will have a greater reduction in reduce subjective craving to smoking cues in a subsequent medication-free cue exposure conducted 24-hours later (CE 2).

Analytic approach: A mixed factorial ANOVA will be used to test whether reduction in craving over the course of CE session 2 significantly differ across groups (CE+ISR vs. CE+PBO). More specifically, a 2X2 mixed (within-between) factorial ANOVA will be conducted with Group (2 levels: CE+ISR vs. CE+PBO) as the between-subject variable and Trials (2 levels: the first and last trials during the CE session 2) as the within-subject variable to examine the Group X Trial interaction effects on craving. A separate analysis (ANCOVA) for the same model will be conducted, controlling for sex and baseline nicotine dependence. In addition, potential moderating roles of sex and baseline smoking severity on the effect of CE+ISR (vs. CE+PBO) on craving at the first trial during the CE session 2 will be explored by using two-way ANOVA to test the Group X Moderator interactions or linear regression models with Group X Moderator interaction terms.

**Specific Aim 2: Feasibility and Acceptability of Implementation:** Descriptive statistics will be calculated for the questionnaire to assess overall clinic staff views of feasibility, acceptability, and ease of implementation. A qualitative descriptive approach will be used to analyze semi-structured interview transcripts using content analysis to systematically code and categorize for trends and patterns in the textual data to remain as close to the staff's experiences as possible. We have successfully used similar approaches in prior studies.

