#### **C3g. Sample size and power considerations**

Based on the sample size calculation using G\*Power, a total sample size of 102 (n=51 for each group) will be sufficient to detect a small effect size ( $f=0.1$ ) in Group (between-subject) by Trial (within-subject: craving ratings for the first and last trials during CE session 2) interaction on craving using mixed (within-between) factorial ANOVA/ANCOVA, with 80% power, an alpha of 0.05, and a correlation coefficient between repeated measures (the first and last trial) of 0.75.

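### The plan gives different covariate rules for the Aim 1 Group x Trial test and does not say which model decides the aim

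*Combined protocol and SAP*

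**What the plan says.** Four places in the combined protocol and SAP bear on the Aim 1 model.

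- **Data Analyses, Specific Aim 1.** The test comes first without covariates: "A mixed factorial ANOVA will be used to test whether reduction in craving over the course of CE session 2 significantly differ" between the groups, using the first and last trials of that session. Then: "A separate analysis (ANCOVA) for the same model will be conducted, controlling for sex and baseline nicotine dependence". The section does not say whether covariates enter as main effects only or also interact with Trial.
- **Measures of smoking behavior, nicotine dependence, withdrawal symptoms, and sleep measures.** The FTND paragraph says the instrument quantifies nicotine dependence, "which will be used as a covariate in the primary analyses". Sex is not mentioned there. The sleep paragraph says the sleep measures "may also be used as a covariate in primary analyses". It also says "a short self-report sleep diary will be administered in order to record the previous night's sleep", and that "the Sleep Diary will be collected at CE visits 1 and 2".
- **Randomization.** Before the analyses, a member of the team will "check the balance of randomization and control for any factors that are imbalanced". No factor list, test or threshold is given.
- **C3g. Sample size and power considerations.** The calculation is for the "interaction on craving using mixed (within-between) factorial ANOVA/ANCOVA", which covers both models without choosing.

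**The concern.** Read alone, the Aim 1 section puts the unadjusted ANOVA first. That does not fit with FTND being a covariate in the primary analyses, and the Randomization rule would change the ANOVA whenever a factor is judged imbalanced. The decisive model could therefore be unadjusted, adjusted for FTND, adjusted for sex and FTND, or any of these plus whatever factors happen to be imbalanced. The same data can then give more than one answer to the trial's only confirmatory between-group question, with no stated rule for which answer counts.

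Two further points follow.

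- Choosing covariates by observed imbalance selects them for chance differences between arms, not for their relation to craving change.
- The sleep option is not limited to values from before dosing. CE session 2 is 24 hours after the session at which the capsule is given, so the CE 2 diary describes the night after dosing. A model that adjusts for it need not estimate the total drug effect.

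**Working it through.** **1. The plan's own figure.** Inputs from the power section: N=102 (51 per group), f=0.1, correlation 0.75, two trials, alpha 0.05.

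- Noncentrality = f² x N x 2 / (1 − 0.75) = 0.01 x 102 x 2 / 0.25 = 8.16.
- Power of F(1,100) = 0.808. With N=100 it is 0.7997, so 102 is the smallest even total. The stated sample size reproduces.
- As a standardized difference in change: d = 2 x √(8.16/102) = 2 x √0.08 = 0.566.

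**2. When the choice of model matters.** With two trials, the Group x Trial test is the test of group on last-minus-first change. A covariate entered only as a main effect adds the same amount to both trials and cancels from the change. In one simulated data set the interaction p value was 0.101 both without covariates and with main-effect covariates, and 0.162 with covariate x Trial terms. Everything below assumes the covariates act on the change.

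**3. Analytic power of the sex+FTND model.** Assumption, not in the documents: sex and FTND are uncorrelated with each other and each correlates r with change.

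- Residual variance = 1 − 2r². Residual df = 102 − 4 = 98.
- Lost degrees of freedom alone: noncentrality 8.16 on 98 df gives 80.7%.
- Expected chance correlation of two covariates with arm inflates the variance by 99/97 = 1.0206, so noncentrality = 8.16 / [1.0206 x (1 − 2r²)].

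| r | Noncentrality | Power |
|---|---|---|
| 0 | 7.995 | 79.9% |
| 0.1 | 7.995/0.98 = 8.158 | 80.7% |
| 0.2 | 7.995/0.92 = 8.690 | 83.1% |
| 0.3 | 7.995/0.82 = 9.750 | 87.1% |

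With no explanatory value the cost is 80.8 − 79.9 = 0.9 points, of which only 0.1 is degrees of freedom. At r = 0.3 the gain is 87.1 − 80.8 = 6.3 points.

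**4. Simulation at the planned effect.** 12,000 runs per setting, 51 per arm, d = 0.566. For the imbalance rule, six candidate factors were flagged at p<0.05; both figures are assumed because the plan gives none.

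| r | 0 | 0.1 | 0.2 | 0.3 |
|---|---|---|---|---|
| Power, unadjusted | 80.2% | 80.2% | 81.2% | 81.2% |
| Power, imbalance-selected | 79.5% | 79.8% | 80.8% | 81.4% |
| Power, FTND only | 80.1% | 80.4% | 82.1% | 84.1% |
| Power, sex+FTND | 79.5% | 80.3% | 83.1% | 87.4% |
| ANOVA and sex+FTND disagree at 0.05 | 3.0% | 4.2% | 6.6% | 9.7% |
| Only sex+FTND significant | 1.1% | 2.2% | 4.3% | 8.0% |
| Only ANOVA significant | 1.9% | 2.1% | 2.3% | 1.7% |

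Imbalance selection follows the unadjusted test to within a point throughout.

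**5. Type I error.** Each model fixed in advance rejects in 4.2 to 5.3% of null trials. If a trial counts as positive when any of the unadjusted, FTND-only or sex+FTND models is significant, the rate is 5.3 / 5.8 / 6.5 / 7.8% at r = 0 / 0.1 / 0.2 / 0.3. Adding the imbalance-selected model leaves it at about 6 to 8%.

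**6. The CE 2 diary.** If the drug shifted that night's sleep, the adjusted estimate would be 0.566 − slope x shift, where slope is the relation of sleep to craving change. The documents give neither size nor sign. With an assumed shift of 0.5 SD and slope of 0.3 in size, the product is 0.15, and the estimate is 0.416 or 0.716 according to sign.

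**The case against.** The best defence is that the plan does have an order. Specific Aim 1 is the only section that specifies a between-group test, it gives the ANOVA first, and it calls the ANCOVA separate. The FTND sentence speaks of primary analyses in the plural, which could include that ANCOVA. An FTND-only model is an inference from an instrument description that omits sex. The sleep covariate is optional, and neither the Randomization nor the Measures section names Aim 1.

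Much of this is fair. The ANOVA is the natural lead if the Aim 1 section stands alone, and FTND-only is the weakest of the readings. But no section calls the ANOVA primary, the Randomization rule would still alter it, and Aim 1 is the plan's only between-group hypothesis test apart from exploratory moderators, so the other sentences have no other natural target.

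It is also fair that the models differ only if covariates act on the change, that disagreement is just 3 to 4% at r of 0 to 0.1, and that naming the ANOVA as primary would remove the ambiguity equally well. The preference for sex+FTND rests on power, not validity, and appears only if the covariates predict change.

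A reader might go further and infer that the trial's type I error is inflated. The documents do not support that: nowhere do they say the most favourable result will be taken, and each model alone holds its level. Nor do they support reading the CE 2 diary as a planned adjustment, or as one that would reduce the effect. It is an option left open, no drug effect on sleep is shown, and the bias could go either way.

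**Conclusion.** The point holds as an inconsistency to be settled before the data are seen. The covariate rules in the Randomization, Measures and Specific Aim 1 sections do not agree, and no section names the deciding result.

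Its size is modest. With covariates acting on the change and r between 0 and 0.3, the two models named in the Aim 1 section disagree at 0.05 in about 3 to 10% of trials at the planned effect. The 6 to 8% type I error is what an open choice could lead to, not a property of any single planned test. These ranges rest on assumed correlations and, for the imbalance rule, on an assumed factor list and threshold.

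Imbalance selection offers no power over the unadjusted test. The sex+FTND adjustment, already in the plan, costs under one point at worst and gains about 6 to 7 points at r = 0.3. The sample size is unaffected. The change should be made, but the design does not depend on it.

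**What to change.** - **Specific Aim 1:** name one decisive model, namely last-minus-first CE 2 craving change regressed on group, sex and screening FTND. Equivalently, use the 2x2 model with sex x Trial and FTND x Trial terms, and state that form. Report the unadjusted ANOVA as a sensitivity analysis.
- **Measures (FTND paragraph) and C3g:** refer to that same model.
- **Randomization:** replace the imbalance rule with a description of baseline characteristics by arm, and make any further adjustment a sensitivity analysis.
- **Measures (sleep paragraph):** exclude the CE 2 diary from any model of the total drug effect. Use the PSQI or the CE 1 diary only in a sensitivity analysis, and only if recorded before the capsule; the documents place both at CE visit 1 without saying whether before or after it.

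This needs no new data and no change in N. The price is the fall from 80.8% to about 79.9% power if sex and FTND explain nothing, mostly from expected chance correlation of the covariates with arm. In addition, imbalance in an unlisted factor would be handled only in a sensitivity analysis.
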